1.0 BACKGROUND

Women with symptomatic uterine fibroids have limited treatment options. Uterine leiomyoma, or fibroids, are benign smooth muscle tumors that occur in 25% of premenopausal women and cause heavy bleeding, pelvic discomfort or pressure, urinary and bowel dysfunction, and adverse pregnancy outcomes. Major surgery (hysterectomy and myomectomy) is the most common treatment; uterine artery embolization is reserved for women who have completed childbearing, and magnetic resonance guided focused ultrasound ablation is in limited use under research protocols. Many women seek medical management, but there are no FDA approved drugs that decrease fibroid volume and symptoms without causing harm during long-term use.

Letrozole is an aromatase inhibitor (AI) that decreases the synthesis of estrogen by the aromatase enzyme in the ovary and peripheral tissues, including fibroid cells. Fibroids are hormonally responsive tumors that grow with exposure to systemic and local estrogen levels. Letrozole is FDA approved as adjuvant therapy for postmenopausal women with estrogen receptor positive breast cancer. However, letrozole has been used for treatment of a variety of gynecologic conditions including chronic pelvic pain among women with endometriosis and for ovulation induction among women with infertility. Six small studies of AIs have reported a 35-55% decrease in fibroid volume over 8-12 weeks of oral AI treatment.¹⁻⁶ In premenopausal women, low dose letrozole at 2.5mg/day may preferentially inhibit estrogen synthesis in fibroids more than the ovaries, thus avoiding undesirable side effects of systemic hypoestrogenism such as hot flashes and decreased bone density. Letrozole may therefore improve fibroid symptoms without impacting long-term health risks.

Fibroids change volume rapidly in response to fluctuating estrogen levels. Fibroids shrink up to 60% in 3 months among women treated with gonadotropin-releasing hormone agonists (GnRH) that markedly decrease overall serum estrogen by shutting down ovarian hormone production.⁷ But the hypoestrogenism with GnRH use causes hot flashes and rapid loss of bone density. In addition, fibroids regrow to their original volume within 2-3 months after discontinuing GnRH.^{8,9} Therefore, GnRH use is generally limited to short-term use to reduce fibroid volume prior to surgical intervention and cannot serve as long-term medical management.

Fibroids produce estrogen that autoregulates fibroid growth. In premenopausal women, the ovary is the primary source of estrogen production. However, estrogen is also produced locally in fibroid cells through the conversion of androgen by aromatase cytochrome P450 enzyme activity.¹⁰⁻¹² Estrogen has autocrine and paracrine action which results in fibroids demonstrating local control over their own growth.^{13,14}

Aromatase inhibitors rapidly decrease fibroid volume but this effect plateaus after 3 months. Letrozole is a type II, reversible, competitive aromatase inhibitor that rapidly blocks estrogen production in peripheral tissues.^{15,16} In the two trial of letrozole alone for treatment of fibroids, fibroid volume decreased by 45-46% after 3 months of treatment. However, 90% of that volume reduction occurred within 1 month after treatment. This growth pattern indicates that intermittent letrozole dosing may be a viable option for long-term treatment.

Low dose daily letrozole in premenopausal women has few adverse effects. Long-term safety data on letrozole is derived from large trials and meta-analysis of postmenopausal women with estrogen-receptor-positive breast cancer on letrozole for 5 years.^{17,18} In these studies, letrozole has been associated with slightly higher risks of hypercholesterolemia and fractures compared with women taking tamoxifen.

It is not appropriate to presume that these risks would be associated with letrozole use in premenopausal women. Letrozole use in postmenopausal women significantly reduces overall serum estrogen levels because postmenopausal women primarily derive estrogen from conversion in peripheral tissue via aromatase. However, estrogen in premenopausal women is primarily produced in the ovary with secondary production in peripheral tissue. In one study of 16 women premenopausal women taking letrozole 5.0 mg/day for fibroid treatment, estrogen levels did drop significantly after 1 month, though remained in the normal range for premenopausal women¹⁹⁻²¹ women¹, but in a subsequent study of 33 women taking letrozole at a reduced dose of 2.5mg/day, there was no change in any hormone levels including estradiol, FSH, LH, or testosterone.³ Two studies of the AI anastrozol similarly showed no change in hormone levels among premenopausal women undergoing fibroid treatment.^{2,4}

There is some concern that daily letrozole will induce ovarian cysts because it successfully induces ovulation for women with the polycystic ovarian syndrome.¹⁹ This has led to the use of an oral progestin and/or combined oral contraceptive in addition to letrozole to prevent cysts in the treatment of endometriosis.^{22,23} However, fibroids are hormonally responsive tumors so use of exogenous hormones may counteract the beneficial effect of letrozole. In addition, in the study of 33 women on letrozole 2.5mg monotherapy, there was no significant change in ovarian volume or development of ovarian cysts.³

2.0 STUDY RATIONALE

Although there is preliminary evidence to demonstrate a positive effect of AIs on reducing fibroid volume, current studies are insufficient to support widespread clinical use. There are only 2 trials of letrozole monotherapy for fibroids with a total of 56 women; both are open-label, unblinded studies. A randomized, blinded, placebo-controlled trial is needed for an unbiased assessment of letrozole efficacy. In addition, most women with symptomatic fibroids are 35-50 years old and may require many years of treatment until menopause when fibroids regress spontaneously with falling serum estrogen levels. All current AI studies are short-term with only 2-3 months of drug delivery due to lingering concerns that AIs might induce hypoestrogenism among premenopausal women. There are also no studies that evaluate the rate of fibroid regrowth after stopping AIs when fibroid estrogen levels may rapidly rise. If fibroids regrow slowly over several months after stopping AIs, there may be a role for intermittent AI dosing to maximize benefit and minimize harm. Studies are needed to assess the safety profile of letrozole for >3 months of use and to evaluate changes in fibroid volume after letrozole is discontinued.

Our ultimate goal is to conduct a multi-centered, randomized, trial of letrozole versus placebo among women with symptomatic fibroids. This trial will provide gold standard evidence to determine if letrozole results in symptom improvement but offers the advantages of less morbidity and lower rates of recurrence of fibroid symptoms.

To prepare for a future multi-centered randomized trial of letrozole, we will first conduct a controlled pilot study (the PLUM study). The pilot will allow us to assess the feasibility of recruiting and retaining study participants to this drug intervention trial. We will also complete essential preparatory work for a future randomized trial; we will create and test study forms, a manual of operations, and a study database that can be easily adapted for a multi-site trial. The PLUM pilot study will lay the foundation for a successful future study of letrozole as a treatment for uterine fibroids.

The PLUM study will also provide preliminary data on the efficacy of letrozole in treating uterine fibroids. We will use PLUM outcome data to estimate effect sizes and standard deviations to calculate an appropriate sample size for a future randomized trial.

3.0 STUDY OVERVIEW

This is a randomized, blinded, placebo-controlled trial of oral letrozole among 20 premenopausal women with symptomatic uterine fibroids. Participants will be randomly assigned in a 1:1 ratio to either oral letrozole 2.5mg/day for 6 months (Group A) or intermittent dosing with letrozole 2.5mg/day and an identical placebo capsule (Group B). Group B will receive medication dosing as follows: 2 months of placebo, then 2 months daily letrozole 2.5mg/day, then 2 months of placebo (Table 1). This dosing regimen in the two groups will allow for: 1) between group comparisons in month 1 and 2 to assess the efficacy of letrozole compared with a placebo, 2) within-group comparisons in month 3-6 in group B to evaluate the rate of fibroid regrowth after discontinuing letrozole to evaluate the possibility of intermediate dosing and 3) within-group comparisons in group A in month 1-6 to evaluate the safety of long-term letrozole use. This pilot data will be critical for determining the appropriate long-term dosing regimen in a future, larger, full-scale trial of letrozole.

Month	1	2	3	4	5	6
Group A	L	L	L	L	L	L
Group B	P	P	L	L	P	P

We will assess changes in fibroid symptoms, quality of life, and sexual functioning monthly using standardized, validated questionnaires. In addition, at baseline, month 2, 4 and 6, we will assess changes in the following measures:

- 1) fibroid and uterine volume assessed by pelvic ultrasound
- 2) serum follicle stimulating hormone (FSH) and estradiol levels to determine ovarian function

Study participants will be recruited at UCSF. All study data will be stored securely in a HIPAA compliant, secure database monitored by the UC San Francisco Coordinating Center. A data safety and monitoring board will oversee participant safety and protection.

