4.0 STUDY OBJECTIVES

The PLUM study will collect essential preliminary data to guide and inform a future multi-centered, randomized trial of letrozole versus placebo. The 3 primary study goals are:

1. To assess the feasibility of conducting a randomized, placebo-controlled trial of letrozole for premenopausal women with fibroids.
2. To collect pilot data that examines differences in fibroid symptoms, fibroid volume, and hormone levels among premenopausal women who take letrozole compared with a placebo.

These will be between-group analyses in Months 1 and 2 (Group A vs. Group B) that serve as preliminary data on the efficacy of letrozole in a placebo-controlled trial.

3. To collect pilot data that examines changes in fibroid symptoms, fibroid volume, and hormone levels among premenopausal women taking continuous and intermittent letrozole dosing.

These will be within-group analyses as follows: Months 1-6 for Group A, Months 3-6 for Group B. These data will provide preliminary information on the safety of letrozole use beyond 3 months (Group A) and the rate of fibroid regrowth after letrozole is discontinued (Group B).

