Estradiol and follicle-stimulating hormone (FSH) levels will be measured at baseline and the end of month 2, 4 and 6. These hormones will detect the development of hypoestrogenism and assess changes in the hypothalamic-pituitary-ovarian axis that regulate normal menstrual function. All blood draws will be performed by certified phlebotomists in the REI practice.

6.1.D Total Cholesterol

Since hyperlipidemia is a rare side effect of letrozole, total cholesterol will be measured at baseline and month 6. All blood draws will be performed by certified phlebotomists in the REI practice. Approximately 5 ml (1 tsp) will be drawn at Baseline and Month 6 for this test.

6.1.E Other Outcomes

Other outcomes related to study intervention and fibroid symptoms will include measures related to:

Treatment Failure: We will ask participants to report any additional fibroid treatments including medical management for fibroid-related symptoms, myomectomy, hysterectomy, uterine artery embolization, MR Guided Focused Ultrasound, endometrial ablation, dilation and curettage, or any new and emerging fibroid treatments.

Adverse Events

This is the first trial of letrozole monotherapy for >12 weeks among premenopausal women. Therefore, a full range of adverse events will be assessed every 2 months for all body systems including known potential side effects such as hot flashes, myalgias, and fatigue as well as unknown side effects that will be identified by using the open ended question "Have you had any changes to your health that impact your ability to perform your normal activities?". In addition to assessing adverse events monthly during the trial, we will query participants about adverse events 30 days after completing the last dose of medication.

Pregnancy and pregnancy outcomes: In this study pregnancy is considered a Serious Adverse Event. Participants will report all known pregnancies while receiving study medication. For each pregnancy, we will query participants about whether the pregnancy resulted in a miscarriage, abortion, or continued pregnancy. For continued pregnancies, we will ask participants to report obstetric outcomes including gestational age at birth, mode of delivery (vaginal or cesarean), and complications (e.g. placenta previa, placental abruption, preeclampsia).

6.1.F Long-term storage of blood

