7.0 ADVERSE EVENTS

This is the first trial of letrozole monotherapy for >12 weeks among premenopausal women. Therefore, a full range of adverse events will be assessed by using the open ended question “Have you had any changes to your health that impact your ability to perform your normal activities?”. In addition to assessing adverse events monthly during the trial, we will query participants about adverse events 30 days after completing the last dose of medication.

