10.0 STATISTICAL CONSIDERATIONS

Data analysis plan: We will use descriptive statistics to characterize the feasibility and process measures listed in Table 5, with 95% confidence intervals. Changes in UFS-QOL scores, the primary outcome, as well as secondary outcomes including hormone levels and fibroid volume, will be compared using linear mixed models for repeated measures, adjusting for baseline. We will estimate 1) between-group differences in change from baseline to months 1 and 2; 2) changes from baseline to months 1-3 and 4-6 in group A; and 3) changes from month 3 to months 5 and 6 within group B.

Sample size calculations: This is a pilot study with the aim of assessing the feasibility of implementing a definitive letrozole trial. Therefore, we chose a sample size that would be large enough to assess feasibility, but small enough to complete the pilot within a the1 year timeframe and with a limited budget. Accordingly, the study will not have power to detect small treatment effects. In the PROMISe pilot study discussed in Preliminary Studies, the standard deviation of the UFS-QOL SSS was 20, and correlation of baseline with follow-up scores declined from 0.5 at 1 month to nearly zero at 3 months. In the analysis for AIM 2 of between-group differences in the change in UFS-QOL from baseline to 2 months , the sample size of 20 will provide 80% power to detect a between-group difference of 13.4 points in average SSS scores at months 1 and 2, after accounting for short term attrition of 10%. In the analysis for AIM 3, assessing longer term changes in SSS scores within group A, the sample of 15 women have 80% power to detect average changes from baseline to months 1-3 and 4-6 of 16.0 points. In additional analysis for AIM 3, assessing changes from month 3 to months 5-6 in group B, the corresponding minimum detectable effect will be 18 points. Effects of this magnitude are

clinically relevant because 15-20 points is the mean difference in SSS between women with symptomatic fibroids and women without fibroids.

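### The named analyses include no adverse-event summary, and the concurrent placebo months are not used to read short-term tolerability

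*Combined protocol and SAP*

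**What the plan says.** Section 3.0 divides the work between the comparisons. The randomised contrast is for "between group comparisons in month 1 and 2 to assess the efficacy of letrozole compared with a placebo". Safety is given to "within-group comparisons in group A in month 1-6 to evaluate the safety of long-term letrozole use". Section 4.0 repeats the division. Goal 2, the between-group goal, covers "differences in fibroid symptoms, fibroid volume, and hormone levels among premenopausal women who take letrozole compared with a placebo". Under goal 3, the within-group analyses, it says "These data will provide preliminary information on the safety of letrozole use beyond 3 months (Group A").

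Adverse events are nevertheless an outcome. Section 6.1.E lists them, names "known potential side effects such as hot flashes, myalgias, and fatigue", and notes that no earlier trial has given letrozole alone to premenopausal women for more than 12 weeks. Table 2 marks adverse-event assessment at months 1 to 7, with no mark at baseline.

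Section 10.0 plans descriptive statistics with 95% intervals for the feasibility and process measures of Table 5. Changes in UFS-QOL, "as well as secondary outcomes including hormone levels and fibroid volume, will be compared using linear mixed models for repeated measures, adjusting for baseline". It names no adverse-event count, rate, interval or comparison.

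The collection schedule is stated in two ways. Section 6.1.E says "a full range of adverse events will be assessed every 2 months for all body systems", and later in the same section speaks of monthly assessment. Section 7.0 also says "In addition to assessing adverse events monthly during the trial", which agrees with Table 2.

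**The concern.** Hot flashes, muscle aches and fatigue are non-specific and also occur in women not taking the drug. A count from women who are all on letrozole therefore mixes drug effect and background in unknown proportions. The trial has one period that could separate them: months 1-2, when Group A is on letrozole and Group B has had only placebo. The plan uses that period for symptoms, fibroid volume and hormones, but not for these events.

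The pilot exists to inform a larger trial, and section 2.0 gives the safety profile beyond 3 months as one reason for further studies. Carried out as written, the plan would pass on an uncontrolled tolerability figure although controlled data had been collected. It also specifies no interval for that figure, so nothing would show how little a count of zero in about ten women rules out.

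**Working it through.** The documents give no adverse-event rate, power or precision, so there is no planned figure to reproduce. The check has three parts: which comparisons are possible, what Group A alone can show, and what the randomised months can show.

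**Inputs.** 20 women randomised 1:1 (section 3.0), so 10 per group. Short-term attrition of 10% (section 10.0), so 10 × 0.9 = 9 per group. Dosing from Table 1; assessment times from Table 2. Background rates and event counts below are assumptions.

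**1. Comparisons available**

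| Period | Group A | Group B | Use for adverse events |
|---|---|---|---|
| Baseline | none scheduled | none scheduled | no pre-drug reference |
| Months 1-2 | letrozole | placebo, never exposed | randomised, 10 v 10; 20 v 20 woman-months |
| Months 3-4 | letrozole | letrozole | no placebo comparator |
| Months 5-6 | letrozole | placebo after letrozole | carry-over possible in Group B |
| Month 7 | off drug | off drug | follow-up; Group A's only off-drug reading |

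Section 10's within-Group-A contrast is change from baseline. For adverse events it cannot be formed, because Table 2 schedules no baseline assessment. A linear mixed model of change is also not the natural analysis for whether a woman had an event.

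**2. Group A alone.** Let m be the monthly chance of first reporting a symptom with no drug effect. Over six months p = 1 − (1 − m)^6, and the expected number among 10 women is 10p.

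- m = 2%: p = 1 − 0.98^6 = 0.114; expected 1.1; chance that at least 2 of 10 report it, 32%.
- m = 5%: p = 1 − 0.95^6 = 0.265; expected 2.6; chance 79%.
- m = 10%: p = 1 − 0.90^6 = 0.469; expected 4.7; chance 98%.

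If no events occur, the exact two-sided 95% upper limit is 1 − 0.025^(1/n): 1 − 0.025^(1/10) = 0.308 (31%) for 0/10, and 1 − 0.025^(1/9) = 0.336 (34%) for 0/9.

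**3. Months 1-2, A versus B.** The Newcombe 95% interval for d = p_A − p_B uses the Wilson limits (l, u) of each proportion:

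lower = d − √[(p_A − l_A)² + (u_B − p_B)²]; upper = d + √[(u_A − p_A)² + (p_B − l_B)²].

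For 3/10 v 1/10 the Wilson limits are 0.108 to 0.603 and 0.018 to 0.404. Lower = 0.20 − √(0.192² + 0.304²) = −0.16; upper = 0.20 + √(0.303² + 0.082²) = 0.51.

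| Assumed counts | Difference, points | 95% interval |
|---|---|---|
| 3/10 v 3/10 | 0 | −36 to 36 |
| 3/10 v 1/10 | 20 | −16 to 51 |
| 5/10 v 1/10 | 40 | −0.2 to 68 |
| 6/10 v 1/10 | 50 | 8 to 75 |

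Fisher's exact test with 10 per group has about 30% power for 10% v 50%; about 80% power needs a difference near 65 points (5% v 70% gives 81%). Even 6/10 v 1/10 has a two-sided Fisher p of 0.057. The comparison can therefore describe but not test.

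**The case against.** The strongest reply is that the safety aim is long-term use. Section 3.0 says so, and section 4.0 specifies use beyond 3 months. Group B crosses to letrozole in month 3, so no randomised placebo comparator exists for that question and Group A is the only source. This stands. A reader might infer that the plan chose the wrong group for long-term safety; the documents do not support that. What is missing is an additional short-term contrast.

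A reader might also infer that nothing bearing on harm is looked at by group. That is too strong. Estradiol and FSH, measured partly to detect hypoestrogenism (section 6.1.C), are compared between groups in the placebo-controlled months, although section 4.0 labels that comparison efficacy. The safety monitor receives events by blinded study group (section 8.0). But hormone levels do not count hot flashes, myalgias or fatigue, and monitoring is not a final analysis.

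Nor can it be said that no adverse-event analysis exists anywhere. Table 5 is not in the supplied text, and section 10 introduces its secondary outcomes with the word including. An adverse-event item in Table 5 is unlikely from its description, but cannot be ruled out.

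Finally, ten per group is too few for a test. This also stands, and it limits the remedy to counts and intervals. It would be too much to call months 1-2 a primary tolerability comparison.

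**Conclusion.** The point holds in a limited form. Section 10 as supplied names no adverse-event analysis, and sections 3.0 and 4.0 place safety only in within-Group-A comparisons. Short-term tolerability could be read against concurrent placebo in months 1-2, and this is not planned. That conclusion rests on the text alone.

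The size depends on background onset, which the documents do not give. Over the assumed range of 2% to 10% per month, between about 1 and 5 of 10 Group A women would report a given symptom over six months with no drug effect. No passage says that such events will be attributed to letrozole or dismissed, or that zero events will be reported as safe; the plan simply offers no means of telling these apart. The randomised comparison would be imprecise but not confounded with background symptoms. Label: cheap improvement.

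**What to change.** Add to section 10 a descriptive adverse-event table by group and period: months 1-2, 3-4, 5-6 and the month 7 follow-up, for hot flashes, myalgias, fatigue and any adverse event.

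- **Months 1-2:** number of women affected in Group A and Group B, with the risk difference and a small-sample 95% interval (for example Newcombe). No hypothesis test.
- **Later Group A months:** number of women affected with an exact binomial 95% interval, labelled as uncontrolled. Where no events occur, quote the upper limit.
- **Group B, months 5-6:** note that placebo here follows letrozole, so these months are not a clean placebo period.

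Add the months 1-2 comparison to goal 2 in section 4.0, and keep Group A as the source for use beyond 3 months. Reconcile the two-monthly and monthly adverse-event schedules in sections 6.1.E, 6.1.G (Table 2) and 7.0; both include month 2, so the comparison is possible under either.

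The cost is wording and one extra table from data already scheduled, with no added visit or procedure. The downside is wide intervals, which the table shows openly.
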